2.3. Exploratory Objective

Identify potential biomarkers that might help us in the future to develop a blood or urine test that can be used to predict response to therapy and radiation therapy side effects for each individual patient. Perform exploratory correlative analyses on blood and urine circulating tumor DNA and microRNA biomarkers with a focus on treated lesion control, in-brain distant control, and overall survival and their correlation to patient and treatment characteristics. To develop this test, we plan to collect blood, urine and tumor tissue (excess tissue that would normally be discarded), medical history, and treatment information. We will then compare the information from the analyses of the samples between patients that had recurrence or developed side effects to radiation therapy with those patients that did not have their cancer come back or have problems with their radiation treatment. The knowledge about these differences can then potentially be used to develop a blood or urine test to identify who will respond well to treatment, is at higher risk for recurrence, detecting it early if it comes back, or developing radiation side effects before radiation treatment is even started.

3. OUTCOME MEASURES

3.1. Primary Outcome Measure

In-brain distant failure, defined as an actuarial 6-month rate of new parenchymal lesions seen outside the planning target volume of any lesion that received SIB on any post-treatment MRI (in all 3 planes) by 6 months. Follow-up MRIs will be fused with the planning scan using our planning software for this assessment.

3.2. Secondary Outcome Measures

1. Treated lesion control, defined as an actuarial 6-month rate of any new, recurrent, or progressing (as defined by RANO criteria, see Appendix 3) tumor within the planning target volume on any post-treatment MRI by 6 months. Follow-up MRIs will be fused with the planning scan for this assessment.
2. Overall survival, defined as an actuarial 6-month rate of patients still alive regardless of disease status at 6 months.
3. Neurocognitive function change, defined as the change from baseline neurocognitive testing scores at a 6-month time point with respect to the HVLT-R.
4. Health-related quality of life change, defined as the change from baseline quality of life assessment at a 6-month time point with respect to the FACT-Br tool.
5. Performance status change, defined as the change from baseline performance status at a 6-month time point with respect to the KPS clinical assessment tool.
6. Incidence of early and late adverse effects as defined by the CTCAE, at any time point during the study follow-up.

3.3. Exploratory Outcome Measure

Generate data for sample size estimates for a future prospective study.

4. ELIGIBILITY CRITERIA

4.1. Inclusion Criteria

1. Age \geq 18 at time of consent.
2. Ability to provide written informed consent and HIPAA authorization.
3. Pathological diagnosis of any solid tumor histology (from any site in the body).
4. Pathological or clinical/radiographic (i.e., by imaging) diagnosis of brain metastatic tumor lesions.
5. Total volume of lesions $\leq 30 \text{ cm}^3$.
6. Maximum volume of largest lesion $\leq 5 \text{ cm}^3$.
 - a. This volume limit would be equivalent to a largest diameter of about 2.1 cm, assuming a perfect sphere.
7. Not a candidate for or eligible for but refused Gamma Knife radiosurgery.

4.2. Exclusion Criteria

1. Previous radiation to the brain, including WBRT or brain radiosurgery.
2. Life expectancy < 6 months (as estimated per the current ds-GPA, see Appendix 1 for details).
3. For histologies not included in the ds-GPA publications or otherwise noted online at brainmetgpa.com, the PI will use either published or validated data, or the PI's best clinical judgment to determine the patient's expected survival.
4. Inability to comply with treatment per investigator discretion.
5. Inability to complete neurocognitive assessments per investigator discretion.

Of note, tumor lesion number is not an inclusion or exclusion criteria as we are using volume-based criteria instead.

5. **STUDY DESIGN**

This trial is a pilot, Phase 2, sequential two-cohort study designed to test two de-escalated WBRT dose levels and assess their ability to maintain acceptable in-brain distant control. The WBRT dose would decrease as we move forward in the study, both in terms of absolute value and EQD2 (i.e., equivalent dose in 2 Gray fractions, as determined by the linear quadratic radiobiological model). The absolute value of the SIB dose will change with each dose level because the number of fractions delivered will depend on the WBRT dose. As such, the SIB dose will be manipulated such that the EQD2 will remain essentially equivalent despite the difference in the number of fractions delivered. This design will ensure that the only variable is the change in WBRT dose.

The next phase of investigation would depend upon the outcome of this study. If we are able to demonstrate that both treatment levels in this study meet our primary endpoint, it would suggest that we have not yet found the lowest acceptable WBRT dose. As such, we would then consider a similar study in which we lower the WBRT dose further. If we do find the lowest acceptable WBRT dose, we envision that the next step would be an appropriately powered equivalency trial comparing that lowest acceptable WBRT dose with SIB vs standard WBRT alone vs standard radiosurgery alone. Outcomes in this trial would include standard efficacy outcomes, survival outcomes, and neurocognitive outcomes.

6. **PATIENT REGISTRATION**

Potential patients will be identified and recruited per the recommendation of surgeons, medical oncologists, tumor boards, Department of Radiation Oncology, recommendations from outside physicians, or self-referral. No advertisement will be used to recruit subjects. Patients who appear to be eligible for this trial will undergo the Informed Consent Process and be screened for eligibility utilizing the eligibility criteria. Eligible patients who complete the Informed Consent Process will be registered in the OnCore® database and assigned a patient ID number. Regulatory files will be maintained by the Radiation Oncology Research Office. Applicable regulatory documents must be completed and on file prior to registration of any patients.

STUDY PROCEDURES

7.1. Radiation Therapy

Note: Intensity-modulated radiation therapy (IMRT) with volumetric arc therapy capability (VMAT) is required. Static IMRT is also allowed if VMAT is not available at the treating institution provided that planning goals and critical structure constraints are met. Rapid review by the Principal Investigator is required.

7.1.1. Dose Specifications

1. Prescription dose will be according to the following specifications.
 - a. The whole brain planning target volume (PTV-WBRT, which is the whole brain volume minus the PTV tumor volumes without additional margin) will receive the pre-specified dosing schedule based on the study's current dose level (see Table 7-1 below). Treatment will be delivered once daily, 5 fractions per week, with breaks in treatment minimized.

The gross tumor planning target volume (PTV-tumors) will receive the pre-specified dosing schedule based on the study's current dose level, which again has been determined such that the EQD2 will be essentially identical (see table below). Treatment will be delivered as a simultaneous integrated boost.

- b. The dose is prescribed such that at least 95% of the PTV-WBRT and PTV-tumors are each covered by at least 95% of its prescription dose. As a point of clarity, each individual lesion with "PTV-tumors" should be covered in this fashion.
 - c. Maximum dose to 2% of the PTV-WBRT (D2%) is 120% of Rx and minimum dose to 98% of the PTV-WBRT (D98%) is 90% of Rx.
 - Maximum dose to 2% of the PTV-tumors (D2%) is 125% of Rx.

- d. Please see section 7.1.6.2 for variations acceptable.

Table 7-1. Study Prescription Dose Table

	WBRT Rx Dose	SIB Rx Dose	# of daily fractions	SIB Dose in EQD2*
Cohort A	25	42	10	49.7 Gy
Cohort B	20	40	8	50.0 Gy
SRS[^]	20 Gy SRS		1	50.0 Gy

Notes: WBRT = whole brain radiation therapy; Rx = prescription; SIB = simultaneous integrated boost; EQD2 = equivalent dose in 2 Gy fractions; SRS = stereotactic radiosurgery.

*For ease of comparison, the SIB dose is converted to the equivalent dose in 2 Gy fractions using the linear-quadratic model of radiation response and assuming an α/β ratio of 10 Gy as is seen in most tumor histologies.

[^]There is no SRS group as a separate study group. This comparison is included to demonstrate that the prescribed SIB doses are similar to a single 20 Gy SRS definitive treatment.

7.1.2. Technical Factors

1. Megavoltage equipment capable of delivering dynamic intensity modulation (using a multileaf collimator or tomotherapy) is required. However, the use of static intensity modulation at centers without dynamic modulation is also acceptable as stated above as long as dose specifications and constraints are satisfied.
2. A megavoltage beam of 6MV or greater must be used, with a minimum source-axis distance of 100 cm.
3. MRI for Radiotherapy

Three-dimensional spoiled gradient (SPGR), magnetization-prepared rapid gradient echo (MPRAGE), or turbo field echo (TFE) axial MRI scan with standard axial and coronal fluid attenuation inversion recovery (FLAIR), axial T2-weighted and gadolinium contrast-enhanced T1-weighted sequence acquisitions will be required to allow for accurate contouring of the hippocampus. To yield acceptable image quality, the MRI scan should use the smallest possible axial slice thickness not exceeding 1.5 mm. The associated coronal and sagittal sequences can be up to 2.5 mm in slice thickness. These imaging sequences should be obtained with the patient in the supine position. The MRI should be obtained within 4 weeks prior to study entry or, if not obtained prior to study entry, within 2 weeks prior to treatment initiation. Immobilization devices used for CT simulation and daily radiation treatments need not be used when obtaining these imaging sequences, but an attempt should be made to image the patient in as close to the same plane as the CT simulation as possible to facilitate fusion of the MRI and CT images.

7.1.3. Localization, Simulation, and Immobilization

1. Patients will be immobilized in the supine position using an immobilization device such as an Aquaplast mask over the head. Patients will be treated in the immobilization device.
2. A non-contrast treatment-planning CT scan of the entire head region using the smallest possible axial slice thickness not exceeding 2.5 mm will be required to define clinical and planning target volumes and hippocampal avoidance regions. The treatment-planning CT scan must be acquired with the patient in the same position and with the same immobilization device as for treatment. This scan should be obtained within 2 weeks prior to initiating treatment.
3. MRI-CT Fusion
The MRI for radiotherapy planning (see Section 7.1.2) and treatment-planning CT should be fused semi-automatically for contouring of targets and normal structures.

7.1.4. Target Volumes

1. The Gross Tumor Volume is defined for the grossly identified lesions on MRI only (GTV-tumors), and encompasses all visible disease seen on MRI as determined by an appropriately trained physician.
2. The Clinical Target Volumes (CTV) are defined per the following specifications.
 - a. For whole brain treatment, CTV-WBRT is defined as the whole brain parenchyma to C1 (if there is no evidence of posterior fossa metastasis) or C2 (if there is MRI evidence of posterior fossa metastasis).
 - b. For gross tumor treatment, CTV-tumors is the same as GTV-tumors. In other words, there is no contour expansion difference from GTV to CTV.
3. The Planning Target Volumes (PTV) are defined per the following specifications.
 - a. For whole brain treatment, PTV-WBRT is the same as CTV-WBRT. In other words, there is no contour expansion difference between CTV and PTV.
 - b. For gross tumor treatment, PTV-tumors is the CTV-tumors contour with a 2 mm uniform expansion in all directions.

7.1.5. Critical Structures

1. The lenses, orbits, optic nerves, optic chiasm, cochlea, pituitary, brainstem, and hippocampi will be contoured as per the experience of the dosimetrist on the case or

the treating physician (in particular, for the hippocampi). Care should be taken to minimize the dose to the lens and orbits. Dose to any point within the optic nerves or optic chiasm cannot exceed 37.5 Gy. Dose to the hippocampi will be noted and recorded but should not change any decisions regarding treatment planning.

2. Please refer to the RTOG hippocampal contouring atlas if needed at <https://www.rtog.org/corelab/contouringatlases/hippocampalsparing.aspx>.

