7.1.6. Radiation Therapy Quality Assurance Review

NOTE: PRIOR TO DELIVERING ANY PROTOCOL TREATMENT, all WBRT-SIB treatment plans must be reviewed and approved by the Principal Investigator. WBRT-SIB treatment cannot be initiated until permission has been granted.

1. The Principal Investigator, [name], will perform an RT Quality Assurance Review for each case from all sites before the start of treatment. Plans should include complete data, including the fused planning MRI-planning CT image set with the associated treatment plan with dose-volume histogram (most often in the DICOM-RT format). Plans must be approved by the Principal Investigator prior to treatment initiation.
2. Acceptable Variations
 - a. Plans with up to 5% deviation in the specified dosimetric parameters in sections 7.1.1 and 7.1.7 may be approved by the Principal Investigator at his discretion.
3. Review Process and Unacceptable Deviations

Treating physicians may be required to modify MRI-CT fusion and repeat the WBRT-SIB planning. Resubmission of the new treatment plan with revised contours does not require review to occur prior to WBRT-SIB initiation UNLESS requested by the Principal Investigator. This determination will be made at the time that unacceptable deviations are communicated to the treating physician.

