7.1.7. Critical Structure Constraints

Table 7-2. Critical Structure Constraints

Structure	Dose constraint	
Optic nerves and chiasm	D_{max}	34 Gy
Cochlea	D_{max}	32 Gy
Pituitary	D_{max}	36 Gy
Brainstem	D_{max} < 5 cc	44 Gy > 37.5 Gy

*Assuming α/β ratio of 2 for CNS normal structures and highest dose per fraction scenario (i.e., 8 fractions).

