12. PATIENT CONSENT AND PEER JUDGMENT

The protocol and informed consent form for this study must be approved in writing by the appropriate Institutional Review Board (IRB) prior to any patient being registered on this study.

Changes to the protocol, as well as a change of principal investigator, must also be approved by the Board. Records of the Institutional Review Board review and approval of all documents pertaining to this study must be kept on file by the investigator (housed in the Radiation Oncology Clinical Trials Office) and are subject to inspection at any time during the study. Periodic status reports must be submitted to the Institutional Review Board at least yearly, as well as notification of completion of the study and a final report within 3 months of study completion or termination.

The study will be conducted in compliance with ICH guidelines and with all applicable federal (including 21 CFR parts 56 & 50), state or local laws.

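### Section 7.1.5 and Table 7-2 give different maximum doses for the optic nerves and chiasm (37.5 and 34 Gy), and the unqualified 37.5 Gy is too loose for the 8-fraction cohort

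*Combined protocol and SAP*

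**What the plan says.** Section 7.1.5, which lists the structures to contour, includes a dose rule: "Dose to any point within the optic nerves or optic chiasm cannot exceed 37.5 Gy". It names no cohort and no number of fractions.

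Section 7.1.7 (Table 7-2) covers the same structures in its first row: "Optic nerves and chiasm D_{max} 34 Gy". The table's footnote assumes α/β = 2 for normal CNS tissue and the "highest dose per fraction scenario (i.e., 8 fractions"). In the text available the footnote's asterisk has no visible anchor, but the table carries no cohort label and reads as one set of limits for the trial.

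Section 7.1.6 gives the tolerance: "Plans with up to 5% deviation in the specified dosimetric parameters in sections 7.1.1 and 7.1.7 may be approved" at the Principal Investigator's discretion. It does not mention 7.1.5. The same section requires the Principal Investigator to approve plans before treatment, but says of replanned cases: "Resubmission of the new treatment plan with revised contours does not require review to occur prior to WBRT-SIB initiation", unless the Principal Investigator asks for it.

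Table 7-1 gives the schedules. Cohort A receives 25 Gy whole brain with a 42 Gy boost in 10 fractions. Cohort B receives 20 Gy with a 40 Gy boost in 8 fractions.

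**The concern.** Both figures are point maxima for the same organs, and they differ by more than the protocol's tolerance can absorb. A planner working from 7.1.5 alone could submit an optic maximum between 35.7 and 37.5 Gy. That plan would satisfy 7.1.5 yet fail Table 7-2 even with the full allowance. No sentence says which limit governs, or that one is a planning goal and the other an absolute stop.

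What is at stake is a stated safety limit, not an inference. The limits bind mainly when a boosted lesion lies close to the optic apparatus. There the optic limit decides how far boost coverage must give way, and the protocol offers two answers. Eligibility (sections 4.1 and 4.2) does not exclude lesions in that position.

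**Working it through.** **Inputs.** Optic limits of 37.5 Gy (7.1.5) and 34 Gy (Table 7-2). Allowance 5% (7.1.6). α/β = 2 (Table 7-2 footnote). Fractions n = 10 in Cohort A and 8 in Cohort B (Table 7-1).

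**Formula.** EQD2 = D × (D/n + α/β) / (2 + α/β).

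**Reproducing the plan's own figures.** With α/β = 10, the formula returns the boost column of Table 7-1:
- 42 Gy in 10: 42 × 14.2/12 = 49.7 Gy
- 40 Gy in 8: 40 × 15/12 = 50.0 Gy
- 20 Gy in 1: 20 × 30/12 = 50.0 Gy

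The optic limits come with no derivation or target EQD2, so they cannot be reproduced in the same way.

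**Does the allowance close the gap?** 34 × 1.05 = 35.7 Gy, which is below 37.5 Gy. In physical dose, 37.5/34 = 1.103, about twice the permitted deviation.

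**Does fractionation explain it?** With α/β = 2, EQD2 = D × (D/n + 2)/4:

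| Physical dose | 8 fractions (Cohort B) | 10 fractions (Cohort A) |
|---|---|---|
| 34 Gy | 34 × 6.25/4 = 53.1 Gy | 34 × 5.40/4 = 45.9 Gy |
| 35.7 Gy | 35.7 × 6.4625/4 = 57.7 Gy | 35.7 × 5.57/4 = 49.7 Gy |
| 37.5 Gy | 37.5 × 6.6875/4 = 62.7 Gy | 37.5 × 5.75/4 = 53.9 Gy |

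The informative comparison runs across the columns: 37.5 Gy in 10 fractions against 34 Gy in 8 is 53.906/53.125 = 1.015. Solving for equal effect, 34 Gy in 8 fractions corresponds to 37.2 Gy in 10, and 37.5 Gy in 10 corresponds to 34.3 Gy in 8.

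**Size against the table's 8-fraction basis (53.1 Gy).**
- Cohort A at 37.5 Gy: +1.5%.
- Cohort B at 37.5 Gy: 62.695/53.125 = 1.180, so +18.0%. Against the table limit with the allowance it is 62.695/57.678 = 1.087, so +8.7%.

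**Who can reach the band?** Section 7.1.1 says "Maximum dose to 2% of the PTV-WBRT (D2%) is 120% of Rx", which is 1.20 × 25 = 30 Gy in Cohort A and 1.20 × 20 = 24 Gy in Cohort B. Whole-brain dose is therefore generally well below 34 Gy. The boost is not: 95% of each tumour volume must receive 95% of prescription, which is 0.95 × 42 = 39.9 Gy or 0.95 × 40 = 38 Gy. Both exceed either optic limit.

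**The case against.** The strongest reply is that nothing contradictory is being ordered. Both figures are upper bounds, and a plan at or below 34 Gy meets both. Section 7.1.5 is mainly about contouring, 7.1.7 is the section devoted to constraints, and the tolerance in 7.1.6 points to 7.1.7 and not to 7.1.5. The structure therefore favours the table. This stands, and it is why the table is the sensible default, but no sentence states the hierarchy. A two-tier reading (planning constraint plus outer stop) is possible. On that reading 7.1.6 already limits what can be approved to 35.7 Gy, so the 37.5 Gy stop would have no function.

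Fractionation also counts for the plan: the near match between 37.5 Gy in 10 and 34 Gy in 8 suggests that the higher number may be a legitimate Cohort A limit. This remains an inference. Section 7.1.5 is not restricted to Cohort A, and 37.5 Gy also appears in the brainstem row of Table 7-2, so the match alone does not settle where the number came from.

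Review is a further protection. The Principal Investigator sees each initial plan and decides, when returning one, whether to see it again. That reduces the replan gap without closing it, and a review still needs one criterion.

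Four stronger readings are tempting and are not supported:
- That the excess is about equal in both cohorts. Comparing 37.5 with 34 Gy within one schedule does give +17.4% in Cohort A (53.9/45.9) and +18.0% in Cohort B. The Cohort A figure matters only if 34 Gy was also the intended 10-fraction limit, and the footnote describes an 8-fraction basis.
- That only boosted lesions can be affected. D2% is not a maximum, because 2% of the whole-brain volume may exceed it. Boosted lesions are the main route, not provably the only one.
- That 34 Gy must be right for both cohorts. The documents do not settle this.
- That patients have been over-treated. The documents give no plan data.

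**Conclusion.** The inconsistency is real, and neither the 5% allowance nor any stated cohort restriction resolves it. The 37.5 Gy sentence is too loose for Cohort B, where it allows an EQD2 18% above the table limit. In Cohort A it lies about 1.5% above the table's 8-fraction basis and may be what was intended.

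These sizes rest on the linear-quadratic model with the protocol's own α/β of 2, and on reading the footnote as the basis of the optic row. They are relative to the protocol's table and imply no outside tolerance.

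The number of plans between 34 and 37.5 Gy cannot be estimated from the documents, but the narrow route to that band suggests few. Cohort B opens only if Cohort A passes the interim rule (section 10.11). No endpoint, sample size or analysis population is affected. The point is minor. Confidence is high for the mismatch itself and lower for the origin of 37.5 Gy.

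**What to change.** **Default.** Replace the 37.5 Gy sentence in 7.1.5 with a reference to Table 7-2 (maximum 34 Gy, subject to the 5% allowance in 7.1.6). This leaves the table as it is.

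**Alternative.** If the sponsor confirms that 37.5 Gy was meant for 10 fractions, state one limit per cohort in Table 7-2 (about 37 Gy for Cohort A and 34 Gy for Cohort B) and refer to it from 7.1.5. The sponsor should then also say whether the allowance applies to the Cohort A figure, because 37 × 1.05 = 38.85 Gy would exceed the present 37.5 Gy stop.

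**Recheck.** Compare stored plans, including replans that were not reviewed again, with the limit that applies to their cohort. Any Cohort B plan with an optic maximum above 35.7 Gy comes first.

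**Cost.** One sentence, or one sentence and one table row, with approval under section 12: "Changes to the protocol, as well as a change of principal investigator, must also be approved by the Board". The default has a possible price in Cohort A. At 34 Gy in 10 fractions the EQD2 is 45.9 Gy, about 14% below the table's 8-fraction basis (1 − 45.9/53.1), so it could remove a valid 10-fraction limit and cost some boost coverage near the optic apparatus. Sponsor confirmation before the edit avoids that. The recheck should need only the dose-volume histograms already required with each plan.
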